# **1** Abbreviations

AE	Adverse Events
BAPE	Benign Asbestos Pleural Effusion
BTS	British Thoracic Society
CI	Chief Investigator
CL	Confidence Interval
CRF	Case Report Forms
CRP	C-Reactive protein
СТ	Computed Tomography
CTU	Clinical Trials Unit
CXR	Chest X-Ray
DNA	Deoxyribonucleic Acid
IPC	Indwelling Pleural Catheter
LAT	Local Anaesthetic Thoracoscopy
LHD	Lactate Dehydrogenase
MDT	Multi-disciplinary Team Meeting
MPM	Malignant Pleural Mesothelioma
NHS	National Health Service
PACS	Picture Archiving and Communications Systems
PIS	Patient Information Sheet
PI	Principle Investigator
PM	Pleural Malignancy
QEUH	Queen Elizabeth University Hospital
RES	Research Ethics Committee
ROS	Reactive Oxygen Species
SAE	Serious Adverse Events
TUS	Thoracic Ultrasound
VATS	Video-assisted Thoracoscopic Surgery

# 2 Synopsis

Study Title	The Meso-ORIGINS Feasibility Study
Study Design	Multi-centre prospective feasibility study incorporating a retrospective multi-centre cohort study
Study Participants	Patients with Benign Asbestos Pleural Effusion (BAPE)
Sample Size	Prospective observational study: n = 54 (or n=27 feasible patients, whichever is reached first). Retrospective cohort study: n=300
Study Period	12 months
Sponsor	NHS Greater Glasgow & Clyde
Background and Rationale	MPM typically develops 30-50 years after inhalation of asbestos and is often presaged by radiological +/- clinical evidence of chronic pleural inflammation, and frequently by overt pleural effusion. The base agnostic pattern of DNA damage recently reported in MPM also suggests a prominent role for immune or inflammatory triggers. However, the recent genomic characterisation of MPM (1) poses major questions regarding the pressures that drive MPM evolution, being dominated by loss of tumour suppressors, with few protein-altering mutations in known oncogenes (1). Greater understanding of the driving (oncogenic) +/- permissive (immunological) events is required to design effective MPM treatments.
	In a future study called Meso-ORIGINS, we aim to define in vivo the key biological events that drive or permit evolution of MPM. Meso-ORIGINS will involve serial biological surveillance (using circulating markers, imaging +/- repeat pleural fluid and biopsies) over a 2-year period preceding the diagnosis of MPM. This will be achieved by recruitment of 850 patients with BAPE, of whom an estimated 12% (n=100) will develop MPM based on previous data (2). This will facilitate unprecedented surveillance of the key early biological events in MPM tumourigenesis.
	
 
The current feasibility study will address important areas of uncertainty regarding the current Meso-ORIGINS design, including:
 
within a prospective feasibility study, the technical feasibility and patient acceptability of a surveillance protocol including LAT, and alternative strategies limited to blood tests, imaging +/- pleural fluid sampling
 
within a retrospective cohort study, greater precision regarding the sample size estimate (currently n=850). This is based on a single study that reported a 2-year MPM transition rate of 12% (95%CI 4.5% - 26.4%) (2). If the true rate is close to the lower end of this 95% CI this may mandate an unfeasible sample size.
 

	Trial Objectives	Associated End-points
Prospective Feasibility Study	Primary Objective: To determine whether it will be possible to recruit sufficient numbers of eligible patients in a reasonable time frame to Meso-ORIGINS based on the currently proposed surveillance protocol (involving LAT)	
 
Primary End-point: Feasibility, defined as the ability to recruit 27 patients over 12-months (or 14 patients over any 6-month period) meeting the following criteria:
 
They satisfy all Meso-ORIGINS eligibility criteria (see below)
 
They deem the proposed thoracoscopic surveillance program acceptable (see Patient Acceptability Questionnaire)
 
Their study team deem that at least one LAT at/before 6 months is technically feasible (see LAT Technical Feasibility
 

	Secondary Objective: To explore reason(s) for declining consent to surveillance and the acceptability to patients of less invasive surveillance protocols (not involving repeat LAT)	
 
Secondary End-point: Results of a Patient Acceptability Questionnaire including hypothetical consent for alternative surveillance strategies, including:
 
Blood Tests
 
Breath sampling
 
Pleural fluid sampling
 
Imaging only (CXR, CT, MRI)
 

Retrospective Cohort Study	Primary Objective: To determine more precisely the rate of transition to MPM in patients diagnosed with BAPE	Primary End-point: The rate of MPM transition, defined as the number of eligible patients diagnosed with MPM within 2 years of the diagnosis of BAPE divided by the total number of eligible patients.
	Secondary Objective: To identify baseline predictors of transition to MPM, allowing refinement of the current Meso- ORIGINS eligibility criteria	Secondary End-point: A logistic regression model for MPM transition using baseline data as predictors

Eligibility Criteria Prospective Feasibility Study Recruitment, Study Visits &	
 
History pleural
 
CT ima histolog followir atypica
 
Informa
 
Progno
 
Retrospec
 
Histolo benign mesoth
 
≥2 yea
 
Exclusion
 
Histo-/a maligna
 
Pleural plus for the < 2 years for the < 2 years for the < 10 years for 
 
	of asbestos exposu plaques aging compatible with gical diagnosis at bio ng: benign fibrinous il mesothelial prolifer ed written consent osis ≥6months ctive Cohort study gical diagnosis com fibrous pleurisy, nor nelial proliferation rs follow-up complet Criteria: cytological diagnosis ancy infection, empyema e Retrospective Coh follow-up completed follow-up completed eligible patients w	Inclusion Criteria: patible with BAPE including n-specific pleuritis or atypical ed at the point of enrolment of MPM or secondary pleural or granulomatous pleuritis fort Study only: at the point of enrolment vill be approached at outpatient nosis of BAPE (this can be a udy visits will be combined with
Follow up	Visit Visit 1	Timing Day 0	Study Interventions Provision of PIS Consent, Registration Baseline CRF
			Follow-up CRF Acceptability Questionnaire after initial BAPE diagnosis then
Retrospective Cohort Study Case Selection and Data Collection	
 
visit 2 can be combined with visit 1 on day 0.
 
The following data will be recorded retrospectively for all eligible patients using LAT, VAT and ultrasound guided biopsy databases, and electronic health records at the study centres. A data collection form (.x/s) will be provided. All data will be recorded in a linked anonymised format.
 
Baseline clinical data (e.g. imaging, blood results, LAT data)
 
Follow-up data, including any diagnosis of MPM within 2 yrs
 
		
Approvals	Research Informed v Feasibility	Ethics Committee (F vritten consent will b Study participants. will be sought for us	REC) approval will be sought. e documented in all Prospective Caldicott (or equivalent) local e of unconsented data in the

Reimbursement to Sites	Sites will be reimbursed on a per patient basis (£25 per patient completing all prospective study visits, £2 per patient with complete data collection in the retrospective study).
End of Study	Recruitment to the prospective study will terminate after 54 patients have been recruited, after 27 patients have met the primary end-point, or 12 months after study opening, whichever is soonest. The study will end after the last prospective study patient has completed Visit 2.

# 4 Abstract and Study Design

### 4.1 Abstract

MPM typically develops 30-50 years after inhalation of asbestos fibers and is often presaged by radiological and/or clinical evidence of asbestos-related chronic pleural inflammation, and frequently by overt pleural effusion. The base agnostic pattern of DNA damage recently reported in MPM also suggests a prominent role for immune or inflammatory triggers. However, the recent genomic characterisation of MPM (1) poses major questions regarding the pressures that drive MPM evolution, being dominated by loss of tumour suppressors, with few protein-altering mutations in known oncogenes (1). Greater understanding of the driving (oncogenic) +/- permissive (immunological) events is required to design effective MPM treatments.

In a future study called Meso-ORIGINS, we aim to define *in vivo* the key biological events that drive or permit evolution of MPM. Meso-ORIGINS will involve serial biological surveillance (using a protocol involving circulating markers, imaging +/- repeat pleural fluid and biopsies) over a 2-year period preceding the diagnosis of MPM. This will be achieved by recruiting approx. 850 patients with Benign Asbestos Pleural Effusion (BAPE), of whom an estimated 12% (n=100) will develop MPM based on previous data (2). This will facilitate unprecedented surveillance of the key early biological events in MPM tumorigenesis. These will be interrogated for mechanisms and potential druggable targets in a genetically engineered mouse model (GEMM) integrated into the Meso-ORIGINS program.

The current feasibility study will address important areas of uncertainty regarding the current Meso-ORIGINS design, including the technical feasibility and patient acceptability of the proposed surveillance protocol (including Local Anaesthetic Thoracoscopy (LAT)) and the sample size estimate. Alternative strategies for surveillance for transformation to MPM will be explored including imaging, blood tests for biomarkers (3, 4) and breath tests (5, 6, 7). The objectives of the feasibility study are as follows:

**Primary:** To determine whether it will be possible to recruit sufficient numbers of eligible patients in a reasonable time frame to Meso-ORIGINS based on the currently proposed surveillance protocol (involving LAT)

Secondary: To define the sample size estimate for Meso-ORIGINS more precisely

#### 4.2 Lay Summary

Mesothelioma is a cancer most commonly affecting the tissue layers which line the lung and inside of the chest wall (the pleura). It most commonly presents with a collection of fluid surrounding the lung (pleural effusion). Mesothelioma is strongly associated with asbestos exposure, which causes intense inflammation of the pleura, but does not occur until many decades after exposure. Benign Asbestos Pleural Effusion (BAPE) is a non-cancerous condition also associated with asbestos exposure and pleural effusion. However, approximately 12% of patients diagnosed with BAPE

are subsequently diagnosed with Mesothelioma. It is not currently known what triggers the change from benign pleural inflammation to Mesothelioma. The Meso-ORIGINS study aims to define this by performing 2 years of surveillance, collecting measurements from repeat pleural fluid and biopsy samples, repeat blood tests and scans. The aim of this study, the Meso-ORIGINS feasibility study, is to determine whether it will be possible to recruit sufficient numbers of patients to Meso-ORIGINS and to work out whether it will possible to perform all of the repeat tests that might be helpful (including biopsies) and whether patients would agree to have these performed.

### 4.3 Study Design

#### 4.3.1 Study Type

The primary objective will be assessed in a prospective observational study. The secondary objective will be assessed in a retrospective cohort study

#### 4.3.2 Disease and Patient Group Studied

Patients with Benign Asbestos-related Pleural Effusion (BAPE)

#### 4.3.3 Study Centres

The Meso-ORIGINS feasibility study will be a multi-centre prospective feasibility study, incorporating a retrospective multi-centre cohort study. The lead centre will be the Glasgow Pleural Disease Unit, QEUH, Glasgow.

#### 4.3.4 Study Duration

The planned study duration is 12 months. Recruitment to the prospective feasibility study will terminate after 54 patients have been recruited, after 27 patients have been met the primary end-point regarding feasibility, or 12 months after the study opens, whichever is soonest. The prospective study will end once the final patient recruited has completed their 6 month follow up visit (Visit 2).

#### 4.3.5 Study Sponsor

The study is sponsored by NHS Greater Glasgow & Clyde.

#### 4.3.6 Study Funding

This study is part-funded from a grant provided by the June Hancock Mesothelioma Research Fund, part-funded by the Glasgow Clinical Research Facility and part-funded by the Chief Investigator.

#### 4.4 **Prospective Feasibility Study Objectives and End-points**

#### 4.4.1 **Prospective Study Objectives**

The primary objective is to determine whether it will be possible to recruit sufficient numbers of eligible patients in a reasonable time frame to Meso-ORIGINS, based on the currently proposed surveillance protocol (involving LAT).

The secondary objective is to explore reason(s) for declining consent to surveillance and the acceptability to patients of less invasive surveillance protocols (not involving LAT)

#### 4.4.2 **Prospective Study End-points**

The **Primary End-point** shall be Feasibility, defined as the ability to recruit 27 patients from 4 centres over 12-months (or 14 patients over any 6-month period) meeting the following criteria:

- a) They satisfy all Meso-ORIGINS eligibility criteria (see below)
- b) They deem the proposed thoracoscopic surveillance program acceptable (see *4.4.2.1 Patient Acceptability* below)
- c) Their study team deem that at least one LAT at/before 6 months is technically feasible (see *4.4.2.2 LAT Technical Feasibility* below)

This recruitment rate is equivalent to 6.8 patients/centre/year, based on the assumptions that 850 patients will be required for adequate signature differentiation in Meso-ORIGINS and 25 centres will recruit (similar to the DIAPHRAGM study (3)) over 5 years.

It is not considered ethical to directly test feasibility by fully executing the proposed surveillance protocol until the study has proven deliverable, particularly with regard to sample size (*see Retrospective Cohort Study*). Therefore, patient acceptability and technical feasibility will be assessed indirectly.

#### 4.4.2.1 Patient Acceptability

To address this aspect of feasibility, a simple questionnaire will be used to record whether patients would hypothetically consent to LAT (or repeat LAT in some cases) for research purposes.

To address the **Secondary Objectives**, reasons for declining consent will be explored and hypothetical consent sought for alternative surveillance strategies, including:

- o Blood Tests
- o Breath Sampling
- Imaging (Chest X-ray, MRI, CT)
- Pleural Fluid sampling

This will be assessed using established sonographic markers (8) and defined as:

- Sufficient\* pleural fluid to allow safe LAT access or
- Sufficient\* lung-sliding to allow pneumothorax induction prior to LAT

\*In the opinion of the site PI who would perform the LAT

Detailed information regarding recommended ultrasound assessment will be provided for each site.

Note that ultrasound-directed cutting pleural biopsy (9) would be an alternative in Meso-ORIGINS if LAT was not possible. Therefore feasibility of this will be recorded.

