#### 5.2 Rationale for the Meso-ORIGINS Feasibility Study

In a future study, called Meso-ORIGINS, we aim to define the key biological events that drive or permit evolution of MPM by recruiting a large population of patients with BAPE. According to the optimal (but most invasive) Meso-ORIGINS design, the study will utilise sequential LAT biopsies acquired over 2-year period preceding the development of MPM. These will facilitate unprecedented surveillance of the driving (oncological) and/or permissive (immunological) events involved in the development of MPM. The Meso-ORIGINS feasibility study will address important areas of uncertainty with regard to the current Meso-ORIGINS design, particularly the feasibility of the currently proposed surveillance protocol (involving LAT), patient acceptability and the sample size required (currently estimated at 850). Patient acceptance of alternative strategies for surveillance will be explored including imaging, blood tests for biomarkers (3, 4) and breath tests (5, 6, 7).

In a prospective element, the Meso-ORIGINS feasibility study will determine the technical feasibility of LAT based on TUS measurements. A Patient Acceptability Questionnaire will be used to determine patients' views on this and a range of less invasive alternative surveillance strategies. A retrospective cohort study using LAT/VAT and image guided pleural biopsy databases at each site will determine more precisely the subsequent incidence of MPM in patients diagnosed with BAPE. If the true MPM rate is lower than the 12% previously reported (2) this would mandate a larger, potentially unfeasible sample size

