### 10.2 Statistical Analysis Plan

#### **10.2.1 Prospective Feasibility Study**

Results will be reported using simple descriptive statistics. The **Primary Endpoint** shall be met if repeat LAT for research purposes is acceptable to the patient at Visit 2 *and* LAT is technically feasible at Visit 2.

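### The acceptability part of the primary end-point is defined in three different ways, and two of them can count a patient who would refuse the 2-year sequential LAT programme

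*Protocol*

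**What the plan says.** The primary objective (section 4.4.1) is whether enough eligible patients can be recruited to Meso-ORIGINS under the currently proposed surveillance protocol, which involves LAT. Section 5.2 describes the preferred and most invasive version of that protocol: "the study will utilise sequential LAT biopsies acquired over 2-year period preceding the development of MPM".

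Section 4.4.2 sets the threshold at 27 patients from 4 centres in 12 months, or 14 in any 6 months. Besides eligibility, each patient must meet two criteria:

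- (b) "They deem the proposed thoracoscopic surveillance program acceptable", with a pointer to section 4.4.2.1;
- (c) "Their study team deem that at least one LAT at/before 6 months is technically feasible".

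Section 4.4.2.1 says that a simple questionnaire will record "whether patients would hypothetically consent to LAT (or repeat LAT in some cases) for research purposes". Section 10.2.1, which states when the end-point is met, requires that "repeat LAT for research purposes is acceptable to the patient at Visit 2" and that LAT is technically feasible at the same visit.

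Section 4.4.2 also says that carrying out the full programme would not be ethical until the study has been shown to be deliverable, and concludes: "Therefore, patient acceptability and technical feasibility will be assessed indirectly".

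**The concern.** Criterion (b) is one of the conditions that decide whether a patient is counted. Its three descriptions differ in what the patient has to accept: a programme, a LAT (a repeat one for some), or a repeat LAT. Neither the measurement nor the scoring rule mentions a series, a number of procedures or a 2-year duration.

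Two things follow. Sites could score the same answer differently, above all for a patient who has never had a LAT. And a count of 27 could include patients who would agree to one more procedure but not to the programme into which the count is projected. The go-ahead for an 850-patient study would then rest partly on willingness for less than that study asks.

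The secondary objective is also affected. A patient who accepts one LAT but would refuse the series need not appear as a decliner, so the reasons for refusing the series might not be collected.

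**Working it through.** **1. The plan's own threshold.** Inputs from section 4.4.2: 850 patients, 25 centres, 5 years.

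- 850 / 25 / 5 = 6.8 patients per centre per year, as stated.
- 6.8 × 4 centres = 27.2, stated as 27. Half of 27.2 is 13.6, stated as 14.
- Section 10.1.1: 54 × 0.50 = 27, where 50% is described as a maximum.

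The threshold reproduces. It is the recruitment rate that the main study needs, with nothing added for patients who accept a LAT but not the series.

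**2. Who can lack a previous LAT.** Section 6.1 admits patients on compatible CT imaging or on histology, and requires histology only for the retrospective cohort. Sections 7.2 and 7.4.1 allow patients with a radiological diagnosis to be recruited at any stage of follow-up. The baseline CRF collects LAT details only where they apply. Patients without an earlier LAT are therefore part of the prospective population.

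**3. The three definitions applied to the same patient.**

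| Patient | 4.4.2(b): programme | 4.4.2.1: LAT, or repeat LAT for some | 10.2.1: repeat LAT |
|---|---|---|---|
| Previous LAT; accepts the 2-year series | met | met | met |
| Previous LAT; accepts one more, refuses a series | not met | met | met |
| No previous LAT; accepts the series | met | met | unclear: the first research LAT would not be a repeat |
| No previous LAT; accepts one LAT only | not met | met | not applicable as worded |

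Only the first row is scored alike under all three. The second row is the patient who would refuse the programme and can still be counted. The last two rows are where the scoring rule does not fit the patient.

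**4. Direction.** Anyone who accepts the series also accepts a single LAT, so programme acceptors are a subset of single-LAT acceptors. If the question asked is about a single LAT, the count is an upper bound for programme acceptance. Criterion (c) works in the same way: one LAT judged feasible by 6 months is an upper bound for technical feasibility of the series, and nothing after Visit 2 is assessed.

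**5. Size.** The documents give neither the number of research LATs nor any rate of continued acceptance. Purely as an assumption, let q be the share of counted patients who would also be willing and technically suitable for the whole series. If exactly 27 are counted over a full 12 months, 27 × q remain:

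| Assumed q | 27 × q | per centre per year (÷ 4) |
|---|---|---|
| 1.0 | 27 | 6.75 |
| 0.9 | 24.3 | 6.1 |
| 0.7 | 18.9 | 4.7 |
| 0.5 | 13.5 | 3.4 |

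At q = 1 there is no overstatement. For a count of exactly 27, any q below 1 puts the rate further below the 6.8 required. Recruitment also stops as soon as 27 patients qualify, so an early finish would imply a higher rate than the table shows. The table shows that the threshold has no slack. It does not estimate q.

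**The case against.** The strongest reply is that the questionnaire and information sheet are not shown. Section 4.4.2(b) names the programme, the Synopsis refers to the Patient Acceptability Questionnaire for it, and section 4.4.2.1 is only a one-line summary. The form may already set out the full schedule. This stands, and it is why the conclusion is that the end-point may overstate. It does not remove the conflict between the three texts, because criterion (b) defers to 4.4.2.1 and section 10.2.1 says when the end-point is met.

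A reader might go further in four ways that the documents do not support:

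- *That the hypothetical question is itself the fault.* Section 4.4.2 discloses the indirect assessment and gives an ethical reason for it. That reason justifies not performing the LATs. It does not explain asking about less than the programme, since a question about the whole programme exposes nobody to a procedure.
- *That acceptability is tested for a first LAT only.* For patients diagnosed by LAT, a further one is already their second, and section 10.2.1 asks about a repeat. The single-LAT reading applies most to those without an earlier LAT.
- *That the plan falls short of a fixed multi-LAT schedule.* No number of LATs is stated. Section 5.2 ties sequential LAT to the preferred design, the Synopsis leaves repeat biopsies optional, and the Lay Summary speaks of repeat biopsies without mentioning LAT.
- *That any error must favour declaring feasibility.* The subset argument covers LAT only. Section 4.4.2.1 names ultrasound-directed biopsy as an alternative where LAT is not possible and records its feasibility, but such patients do not count towards the 27. For tissue sampling overall, that works in the other direction.

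It is also fair that the primary objective is recruitment, not completion of every procedure, and that later ultrasound access could not be observed with one follow-up visit. This supports leaving criterion (c) as a minimum.

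**Conclusion.** The point holds as a conflict in the definition of the primary end-point. Sections 4.4.2(b), 4.4.2.1 and 10.2.1 set three different tests of acceptability, and the last does not fit eligible patients without a previous LAT. This part needs no assumption.

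Scored by 4.4.2.1 or 10.2.1, a patient who would refuse the sequential 2-year programme can count towards the 27. The end-point may therefore overstate acceptability of that programme and cannot establish it. Whether it does so in practice depends on the unseen questionnaire. How far depends on the share of counted patients who would accept the series, and the documents give no basis for that figure. The figures for q below 1 are illustrations under assumed shares. They should not be cited as an expected shortfall.

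**What to change.** - Use one scoring rule in sections 4.4.2(b), 4.4.2.1 and 10.2.1, worded to apply to patients with and without a previous LAT, for example acceptance of LAT under the currently proposed Meso-ORIGINS programme.
- Have the questionnaire describe that 2-year LAT programme, if it does not already, and score (b) as met only if the programme is accepted.
- Report acceptance of a single LAT separately, as a secondary result. Patients who accept one LAT but not the series can then be asked for their reasons.
- Keep criterion (c) as a minimum, and state that one LAT judged feasible by 6 months is an upper bound for technical feasibility of the series.

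The cost is a revision of three short texts and, where needed, of the questionnaire. No visit or procedure is added. There are two downsides: the primary count may be lower, and the sponsor must state a provisional schedule for a design that this study is meant to inform. The schedule can be labelled provisional, and its content is for the sponsor to decide.
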